3.5. Blinding

There will be no blinding in this study. Randomization will be conducted publicly with all clinic managers and district officials will be invited. Cooperation with program leaders is essential to maximize facility retention in the study.

3.6. Informed consent

Facilities are the subject and unit of analysis in this study. Project Unlocked implementers will approach facilities with an overview of the study and invite them to participate, after having received permission from the Northwest Department of Health. Facilities are free to decline the invitation to participate without repercussion. Facilities interested in participating will be asked for verbal agreement to engage in the study, but this study does not require consent.

No consent is required for this study from either the individual or facility level, as all activities are programmatic in nature and the study involves no data collection (i.e., there will be no primary data collection, as only routinely collected data will be used for the analysis). This is an evaluation of a routinely implemented program. No individuals will be randomized and no individual-level data will be collected for this study. Only aggregate-level program data will be used for the evaluation.

3.7. Participant inclusion and exclusion criteria

Inclusion: Facilities must be in the Northwest Province with Aurum as the PEPFAR implementing partner to be eligible to participate. To be eligible, facilities must have a demonstrated need for administrative and programmatic interns. Facilities must also express a willingness and interest to engaged with Project Unlocked. They must be willing and interested to receive an entire package of interns that fill both administrative and programmatic roles. For facilities to be considered eligible for this study, they must not have previously received interns, other than for administrative support, from Project Unlocked.

Exclusion: Facilities are ineligible if they are not interested in receiving both administrative and programmatic interns, and if they have no demonstrated need for these interns (e.g., the facility already has people placed in roles of self-testers, patient navigator, and patient tracer).

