3.2. Study Location and Population

HIV facilities: This study will primarily be conducted among health facilities in Ngaka Modiri Molema (NMM) district in Northwest Province, for which Aurum is the PEPFAR implementing partner. We selected NMM district because the majority of facilities in this district have not yet participated in Project Unlocked but have expressed interest in the program. There 31 facilities in NMM district currently eligible for this study. These facilities and accompanying details are described in Table 1 (see next page). Project activities will be expanded to facilities in

other districts in Northwest Province if needed for operational reasons or to maintain the power required for this study.

HIV clinics are actively recruited to participate in Project Unlocked. Aurum uses its position as Implementing Partner to identify clinics where additional capacity for non-clinical HIV activities is necessary, and thus identify clinics that could benefit from the Project Unlocked model.

Youth Interns: Project Unlocked passively recruits youth to participate in this project, relying on flyers at community-level health facilities and word of mouth to encourage application to the program. The target youth population for the project is aged 18-30 with low socioeconomic status, minimal education, and limited job experience. The median age of participation is approximately 25 years; youth under 18 are not part of this project. Youth are selected into the program based on the level of need at the HIV clinics in their communities, not based on the youth's skill set or experience.

Table 1. Facilities in NMM district, Northwest Province eligible for inclusion in proposed cluster RCT. Averages were calculated from October 2018-July 2019.

Facility name	Local Municipality	Avg No. Patients / Month	Avg No. Tested/ Month	Avg No. Newly Positive/ Month	Avg No. Initiated/ month	Avg No. Initiated on same day/ month	Total No. On ART (July 2019)	Total No. Default Early (July 2019)
Agisanang Clinic	anang Clinic Tswaing		264	7	7	4	740	76
Bakerville Clinic	Ditsobotla	1075	72	3	4	1	327	67
Blydeville Clinic	Ditsobotla	1244	116	9	8	4	577	99
Blydeville Old	Ditsobotla	1640	209	12	10	5	719	139
Bodibe 1 Clinic	Ditsobotla	3274	501	14	14	10	1181	225
Boikhutso Clinic	Ditsobotla	3907	669	21	20	10	1577	268
Braklaagte	Ramotshere Moiloa	1661	105	5	5	4	536	72
Coligny CHC	Ditsobotla	3033	426	14	14	2	1013	200
Delareyville CHC	Tswaing	2938	416	23	24	17	1331	335

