Dinokana CHC	Ramotshere Moiloa	3593	453	12	14	10	1211	104
Dinokana old	Ramotshere Moiloa	1528	184	6	6	2	702	43
Driefontein	Ramotshere Moiloa	837	85	1	2	1	249	38
Ganalaagte Clinic	Tswaing	2948	244	10	13	6	1254	189
Gopane	Ramotshere Moiloa	1882	226	4	4	0	501	45
Groot Marico	Ramotshere Moiloa	1072	147	6	5	3	494	92
Itekeng Clinic	Ditsobotla	1419	205	4	5	4	526	137
Itsoseng CHC	Ditsobotla	4350	469	13	13	4	1279	191
Itsoseng Clinic	Ditsobotla	1555	105	5	5	2	537	105
Kunana Clinic	Tswaing	1949	141	4	5	0	581	82
Lehurutshe Hospital	Ramotshere Moiloa	1462	184	7	8	1	181	24
Letsopa Clinic	Tswaing	2885	447	12	14	7	966	124
Mokgola	Ramotshere Moiloa	1611	159	4	5	3	486	57
Motswedi	Ramotshere Moiloa	1344	221	5	5	3	485	44
Ntsweletsoku	Ramotshere Moiloa	1034	20	3	6	1	425	86
Ottosdal CHC	Tswaing	2892	255	10	9	4	828	335
Rietpan	Ramotshere Moiloa	750	134	3	4	2	243	18
Sannieshof CHC	Tswaing	1550	97	7	6	3	449	59
Tlhabologang Clinic	Ditsobotla	2475	289	9	9	4	680	211
Tswelelopele CHC	Ramotshere Moiloa	2698	394	13	12	7	1040	98
Vriesgewacht Clinic	Tswaing	1598	145	4	5	3	447	79
Zeerust	Ramotshere Moiloa	1272	271	14	11	10	736	56

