3.3. Study arms

There will be an equal number of facilities in the control and intervention arms (1:1 randomization). Facilities are the unit of analysis and will be randomized to the control or intervention arms. Each participating facility will receive a similar number and allocation of youth interns at the facility for a year.

Control arm: Facilities in the control arm will receive the minimum package for the intervention at baseline, i.e., 1-2 interns who will be assigned to administrative roles, such as admin clerk, file clerk, or data capturer.

Intervention arm: Facilities in the intervention arm will receive the minimum package and the intervention package at baseline. That is, they will receive 1-2 interns placed in administrative roles (admin clerk, file clerk, or data capturer) and 2-3 interns placed in programmatic roles according to the needs of the facility, one of each of the following: self-screener, patient navigator, and/or tracer. The number of interns allocated to the clinic will be based on the size of the clinic; whether the clinic receives two or three program interns, they will cover self-screening, patient navigating, and tracing. Interns engaged in self-screening will provide pre-counselling to patients and support the patient's use of the self-screening kit. The intern will provide a post-counselling session if the patient tests negative or connect them with one of the facility's lay counsellors if the test is positive. (Note: The self-screening test is used only as a screening test and requires confirmation using traditional testing methods if positive, per South Africa's current national protocol.) Interns placed as patient navigators and tracing will support roles as outlined in Figure 1 (see page 2).

We will aim for control and intervention sites will be similar in all essential regards, other than receipt of the intervention package, as all facilities come from a similar geographic region (i.e., NMM district, Northwest province, South Africa) and are similarly managed (i.e., Aurum is the implementing PEPFAR partner for HIV work at each facility). While differences between facilities do exist, randomization of facilities to the control or intervention arms will result in balanced differences between arms and minimize bias. Preliminary data collection at clinics will be done prior to randomization and restriction may be applied based on those results.

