3.4. Randomization of study clinics

All facilities that are eligible and willing to participate in this study (18-24 facilities) will be randomized to the control or intervention arm. We will use stratification improve similarity between facilities in the treatment and control groups. Facilities will be, at minimum, stratified by HIV programmatic performance (measured by HIV testing) and, if necessary, also stratified by size (measured by total monthly head count at the facility). The final decisions for stratification will be driven by the facility data observed in the year proceeding the study. The minimal proposed stratification is outlined in Figure 2.

We will randomize an equal number of facilities to the control or intervention group within each strata using a random number generator. We will randomly assign facilities at a joint meeting between study implementors and program staff (e.g., the NMM health district manager).

[figure not shown]

Figure 2. Allocation of facilities to control or intervention

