5. STUDY OUTCOME

5.1. Primary Outcomes

There are three primary outcomes of interest in this study, which will be assessed for a total of **six months** through a combination of variables that reported monthly through TIER.net to Aurum. The indicators that will be used to assess the primary outcomes of interest are summarized in Table 3 below.

First Outcome: % **Tested for HIV** –Number of individuals who received HIV testing services (HTS) and received their results out of all individuals visiting the clinic for services. This will be calculated through use of two standard indicators.

• % Tested for HIV = HTS_TST / Head Count

Second Outcome: % **Linked to Treatment** – *Number of individuals testing positive who were linked to treatment at the facility, out of all individuals who tested positive for HIV.* There will be two measures we examine:

- % Linked to care on day of testing = Initiated Same Day / HTS TST Pos
- % Linked to care within 14 days of testing = Initiated 14 Days / HTS_TST_Pos

Third Outcome: % **Retained in care** –*Number and percentage of people on treatment for HIV who default from treatment (early default, late default).* There will be two measures we examine:

- % Early Default = ART Default Early / Total on Treatment
- % Default = ART Default Late / Total on Treatment

We will rely on indicators reported through routine reporting mechanisms, primarily relying on TIER.Net due to its monthly frequency of reporting and the high number of indicators included in these reports. The numerators and denominators for each indicator will come from the same reporting period (i.e., the same month).

While the full study is nine months in duration, the first three months will be a "run in" period, data from which will not be used to assess study outcomes. We will use data from months 4-9 (i.e., six months of data) of the intervention period to calculate these outcome measures.

Table 3. Indicators that will be used to measure outcomes of interest are reported monthly through TIER.Net.

Outcome	Indicator	Indicator Definition			
% Tested for HIV	Head Count	Number of individuals visiting the clinic for services			
	HTS_TST	Number of individuals who were tested for HIV			
% Linked to	HTS_TST_POS	lumber of individuals who tested positive for HIV			
Treatment	Initiated Same Day	Number of individuals who were started on ART on the same day they tested positive for HIV			

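### No rule keeps facilities that may serve the same community out of opposite arms, although Table 1 lists three same-name pairs as separate eligible clusters

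*Protocol*

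**What the plan says.** **Eligibility.** The geographic criterion in section 3.7 is "Facilities must be in the Northwest Province with Aurum as the PEPFAR implementing partner to be eligible to participate". The other criteria concern need, willingness and no earlier programmatic interns. None concerns distance, catchment or community.

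**Randomisation.** Section 3.4 states: "All facilities that are eligible and willing to participate in this study (18-24 facilities) will be randomized to the control or intervention arm". Facilities are to be "stratified by HIV programmatic performance (measured by HIV testing) and, if necessary, also stratified by size", and then: "We will randomize an equal number of facilities to the control or intervention group within each strata using a random number generator". Section 3.3 adds that, after preliminary data collection, "restriction may be applied based on those results". That restriction is optional and names no spatial criterion.

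**Table 1 (section 3.2).** Three pairs appear as separate eligible facilities:
- Blydeville Clinic and "Blydeville Old", both in Ditsobotla
- Dinokana CHC and Dinokana old, both in Ramotshere Moiloa
- Itsoseng CHC and "Itsoseng Clinic", both in Ditsobotla

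**Outcomes.** Section 5.1 defines linkage as "Number of individuals testing positive who were linked to treatment at the facility, out of all individuals who tested positive for HIV". Numerator and denominator are one facility's counts for the same month. Sections 3.6 and 6.1 exclude patient-level data. Section 8 lists four limitations; contamination and patient movement are not among them.

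**The concern.** A cluster trial relies on patients staying with the facility whose arm they are counted in. Where two facilities serve one community and are allocated to different arms, that can fail in three ways:

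- **Linkage.** A person who tests positive at one facility and starts ART at the other is a linkage failure in one arm and a surplus initiation in the other. One movement therefore enters the contrast twice.
- **Testing.** A test is credited to the facility attended, so a shift in where people test changes both percentages.
- **Default.** An unrecorded move looks like a default at the facility that was left.

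With 9 to 12 facilities per arm, one split pair supplies 1/12 to 1/9 of each arm. Because the outcomes are aggregates, no analysis can trace who moved. Whatever the statistical analysis plan contains, it cannot undo an allocation already made in public.

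**Working it through.** **1. Chance of a split, from the protocol's own numbers.** Inputs: 31 eligible facilities (section 3.2), N = 18 to 24 enrolled (section 3.4), 1:1 allocation (section 3.3), three pairs (Table 1). Simple allocation is assumed, with k = N/2 per arm.

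- One pair, both enrolled: P(split) = k/(N − 1), which is 12/23 = 52% for N = 24 and 9/17 = 53% for N = 18.
- Stratification does not protect. Two members in one stratum of even size s are split with probability (s/2)/(s − 1), which exceeds 1/2. Members in different strata are split with probability 1/2.
- All six enrolled: the number of allocations with no split pair is the sum over j = 0 to 3 of C(3, j) × C(N − 6, k − 2j).
  - N = 24: 18,564 + 131,274 + 131,274 + 18,564 = 299,676 of 2,704,156, so P(at least one split) = 1 − 0.111 = 89%.
  - N = 18: 220 + 2,376 + 2,376 + 220 = 5,192 of 48,620, so 1 − 0.107 = 89%.
- Enrolment as a random draw from 31 (an assumption): P(one given pair enrolled and split) = N(N − 1)/(31 × 30) × k/(N − 1), which is 0.594 × 0.522 = 0.310 for N = 24 and 0.329 × 0.529 = 0.174 for N = 18. For at least one of three pairs, exact enumeration gives 68% and 44%. Treating the pairs as independent gives nearly the same: 1 − 0.690³ = 67% and 1 − 0.826³ = 44%.

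**2. What a given flow would do to linkage (illustration only).** The protocol gives no transfer rate. Assume 80% linkage at both members, equal sizes, no true effect, and a share f of one member's positives starting ART at the other instead of at their own facility. The two percentages become 80 − 100f and 80 + 100f, a gap of 200f points. Dividing by 12 or 9 gives the shift in an unweighted arm difference per split pair.

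| f | Percentages | Gap (points) | Shift per split pair (points) |
|---|---|---|---|
| 2% | 78 v 82 | 4 | 0.3 to 0.4 |
| 5% | 75 v 85 | 10 | 0.8 to 1.1 |
| 10% | 70 v 90 | 20 | 1.7 to 2.2 |

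The sign depends on which way people move. The pairs are not equal in size (monthly new positives 9 and 12, 12 and 6, 13 and 5 in Table 1), and section 7.1 plans inverse-variance weights, so these are orders of magnitude only.

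**3. Does Table 1 show movement within the pairs?** Average initiations exceed average new positives in 13 of 31 facilities (272 against 264 in total). For the six paired facilities:

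| Facility | New positives | Initiated |
|---|---|---|
| Blydeville Clinic | 9 | 8 |
| Blydeville Old | 12 | 10 |
| Dinokana CHC | 12 | 14 |
| Dinokana old | 6 | 6 |
| Itsoseng CHC | 13 | 13 |
| Itsoseng Clinic | 5 | 5 |

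No pair has an excess at one member and a deficit at the other. Nine of the 13 excesses are a single unit in rounded averages.

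**4. Power, for scale.** Table 4 reproduces. The design effect is 1 + ((cv² + 1)m − 1) × ICC. With cv = 0.596, m = 1,687 and ICC = 0.01 it is 23.85. Effective n per arm is 12 × 1,687/23.85 = 849, and power for 0.14 against 0.19, two-sided 5%, is 79%.

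- **If contamination only diluted the testing effect.** Suppose a share c of each split pair's patients receives the other arm's exposure (assumed). The effect shrinks by the factor 1 − (pairs/12) × 2c. With three split pairs, c = 5%, 10%, 20% and 30% gives power of 77%, 75%, 71% and 66%. With one split pair it is 79%, 78%, 77% and 75%.
- **If three pairs were merged.** 24 clusters become 21, or 10.5 per arm on average. Effective n is 743 and power about 74%.

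**The case against.** The strongest reply is that a shared catchment is inferred from names alone. That stands: the risk is conditional on a fact the protocol does not give.

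A reader might infer that movement favours the intervention on linkage and dilutes testing and retention. The document does not support a direction. People drawn to the intervention facility for testing and not retested at the control facility would lower the control percentage and widen the difference. A silent move from control to intervention would count as a control default and also widen it, while the reverse move would narrow it. Linkage can go either way too.

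A reader might also take the initiation excess in Table 1 as proof of movement. It is not. The paired facilities do not show the pattern, 12 of the 13 facilities with an excess have no same-name partner, earlier diagnosis is another explanation, and the Table 1 column has no 14-day limit.

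Two further points hold. Same-day linkage is much less exposed, because a patient would have to test and start at different facilities on one day. And merging pairs can cost about as much power as moderate dilution would.

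Finally, sections 3.3 and 3.4 leave room for restriction and defer the final stratification. That makes the repair easy, but neither section names place or catchment, so the gap remains.

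**Conclusion.** The concern holds as an unguarded design risk, not as a demonstrated bias. The protocol lets facilities with the same place name and municipality enter as separate clusters and fall in opposite arms. A split is likely: 44% to 89%, depending on how many facilities, and which, enrol. These figures assume simple 1:1 allocation, and the lower two (44% and 68%) also assume enrolment at random from the 31. If members of a split pair share a catchment, 14-day linkage, testing and default can each be biased in either direction, and the planned data cannot reveal it. The size cannot be stated from the document. Table 4 is not in error and is not affected. Correction before allocation is warranted because it is cheap then and impossible afterwards.

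**What to change.** 1. **Section 3.7.** Before the randomisation meeting, have the district confirm which listed facilities serve the same community, checking at least the three named pairs. From each confirmed pair, enrol only one facility. Removing one of each leaves 31 − 3 = 28 for at most 24 places.
2. **Section 3.4, if too few facilities are willing.** Either constrain the randomisation so that both members of a confirmed pair fall in the same arm, or randomise and analyse the pair as one cluster.
3. **Section 8.** List possible movement between neighbouring facilities as a limitation.

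**Cost.** The district manager is already expected at the randomisation meeting, so confirmation needs only a question asked beforehand. Enrolling one per pair loses no clusters if 24 of the 28 are willing. Keeping three pairs together leaves about 11% of the possible allocations (299,676 with 24 facilities, 5,192 with 18, before stratification). Merging removes up to three clusters (24 to 21), with power falling from roughly 79% to 74% at ICC 0.01, and an odd total conflicts with the equal-arms rule. If the district finds that a pair does not share a community, nothing changes for that pair.

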4. STUDY PROCEDURES

4.1. Procedures common to patients in both control and intervention arms

All facilities in this study will retain their normal staff and receive the support of a minimum package of administrative interns from Project Unlocked. The minimum package consists of 1-2 interns that will fill roles of admin clerk, file clerk, and/or data capturer. It is important that all participating facilities receive this minimum package to ensure similar data quality between the intervention and control groups.

The analysis for this evaluation utilizes routinely collected data. We understand that the addition of staff who serve in administrative roles, such as data capturers or file clerks, can impact the quality of data. To understand the impact that interns have on HIV services, it is imperative that both the control and treatment facilities have a similar level of data quality. As such, both the treatment and control facilities will receive this minimum package of administrative interns. Aurum will provide additional support to supervise data capture at both intervention and control sites, if it is necessary to ensure data are being routinely captured at all sites.

Ensuring the control and intervention group both receive a minimal package of interns will also serve to increase willingness to participate in this study, as all facilities will be assured a base number of interns at baseline.

4.2. Procedures specific to intervention arm

The intervention arm will receive an intervention package that consists of 2-3 interns assigned to the roles of self-screener, patient navigator, and patient tracer. These roles are directly responsible for HIV testing, linkage

to care, and retention in care, respectively (see Figure 1). The exact number of interns at an intervention facility may differ based on the size and needs of the facility. However, the interns placed at the facility will cover these three roles, with one intern being able to occupy more than one role, if necessary.

At nine months the study will conclude, at which time the control facilities will also be offered the treatment package (i.e., 2-3 programmatic interns). The difference in staff between the control and treatment facility is summarized in Table 2 below.

Table 2. Comparison of procedures between control and treatment facilities.

Control Facility	Treatment Facility
Routine Staff + Administrative Interns (File clerk, admin clerk,	Routine Staff + Administrative Interns (File clerk, admin clerk,
and/or data capturer)	and/or data capturer) + Program interns covering the roles of
	self-screener, patient navigator, and patient tracer

5. STUDY OUTCOME

5.1. Primary Outcomes

There are three primary outcomes of interest in this study, which will be assessed for a total of **six months** through a combination of variables that reported monthly through TIER.net to Aurum. The indicators that will be used to assess the primary outcomes of interest are summarized in Table 3 below.

First Outcome: % **Tested for HIV** –Number of individuals who received HIV testing services (HTS) and received their results out of all individuals visiting the clinic for services. This will be calculated through use of two standard indicators.

• % Tested for HIV = HTS_TST / Head Count

Second Outcome: % **Linked to Treatment** – *Number of individuals testing positive who were linked to treatment at the facility, out of all individuals who tested positive for HIV.* There will be two measures we examine:

- % Linked to care on day of testing = Initiated Same Day / HTS TST Pos
- % Linked to care within 14 days of testing = Initiated 14 Days / HTS_TST_Pos

Third Outcome: % **Retained in care** –*Number and percentage of people on treatment for HIV who default from treatment (early default, late default).* There will be two measures we examine:

- % Early Default = ART Default Early / Total on Treatment
- % Default = ART Default Late / Total on Treatment

We will rely on indicators reported through routine reporting mechanisms, primarily relying on TIER.Net due to its monthly frequency of reporting and the high number of indicators included in these reports. The numerators and denominators for each indicator will come from the same reporting period (i.e., the same month).

While the full study is nine months in duration, the first three months will be a "run in" period, data from which will not be used to assess study outcomes. We will use data from months 4-9 (i.e., six months of data) of the intervention period to calculate these outcome measures.

Table 3. Indicators that will be used to measure outcomes of interest are reported monthly through TIER.Net.

Outcome	Indicator	Indicator Definition			
% Tested for HIV	Head Count	Number of individuals visiting the clinic for services			
	HTS_TST	Number of individuals who were tested for HIV			
% Linked to	HTS_TST_POS	lumber of individuals who tested positive for HIV			
Treatment	Initiated Same Day	Number of individuals who were started on ART on the same day they tested positive for HIV			
	Initiated 14 Days	Number of individuals who were started on ART within 14 days of testing positive for HIV			
% Retained in	TX_Curr	Number of individuals currently receiving ART at the facility			
Care	ART Default Early	Number of individuals who missed treatment within the first 28 days after initiation			
	ART Default Late	Number of individuals who missed treatment after 28 days from date of initiation			

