HIV, % linked to treatment, and % retained in care in each facility for the six months of the intervention period. We will calculate this by aggregating each indicator, then calculating the outcomes of interest (percentages) based on the six-month total counts. In the second step, we will carry out weighted 2-sample t-tests to test the null hypothesis that there is no significant difference between the intervention and the control groups with respect to these summary measures. Weighted approaches are preferred here, as they have been shown to improve efficiency when clusters are not of the same size [24], which is the case in our trial. In our approach, the weights are set to be the inverse of the estimated variance of the cluster summary measures, that is,

$$w_i = \frac{1}{v_i + \sigma^2}$$

where v_i is the variance of the cluster level summary for facility i and σ^2 is the between-cluster (between-facility) variance. We will also conduct additional analyses adjusting for facility-level factors as necessary.

Should changes in testing, linkage to care, and retention in treatment be noted in the analysis, we will descriptively examine these indicators by sex and age groups of interest to understand what demographic was receiving additional testing and/or care as a result of this program. These indicators are available in aggregate in the routinely reported data.

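### The Table 3 definition of early default does not reconcile, as a monthly count, with the early-default totals in Table 1, so a primary retention measure is not determined

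*Protocol*

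**What the plan says.** Section 5.1 makes retention in care the third primary outcome and measures it by two default percentages. Section 2.2 uses retention as the proxy for viral suppression.

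- **Early default (Table 3):** "Number of individuals who missed treatment within the first 28 days after initiation".
- **Late default (Table 3):** "Number of individuals who missed treatment after 28 days from date of initiation".
- **Denominator, TX_Curr (Table 3):** "Number of individuals currently receiving ART at the facility".
- **Formula (section 5.1):** % "Early Default = ART Default Early / Total on Treatment".
- **Timing (section 5.1):** "The numerators and denominators for each indicator will come from the same reporting period (i.e., the same month".
- **Aggregation over months 4-9 (section 7.1, Statistical analyses):** "We will calculate this by aggregating each indicator, then calculating the outcomes of interest (percentages) based on the six-month total counts".

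Table 1 in section 3.2 gives baseline figures for the 31 eligible facilities. They include average ART initiations per month (October 2018 to July 2019), the number on ART in July 2019, and a column headed "Total No. Default Early (July 2019".

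**The concern.** Read literally, Table 3 lets a patient become an early defaulter only during the first four weeks of ART. In any one month the numerator can then come only from recent initiates, a small group. Table 1 reports early-default totals far larger than that group. The indicator described in Table 3 therefore does not appear to be the one that the routine reports supply.

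The protocol itself fixes the definition, the formula and the aggregation, so an analyst who follows it cannot tell which quantity is being estimated:

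- **Literal 28-day reading.** The numerator is drawn from new initiates and the denominator is everyone on ART. The percentage then moves with the number of initiations even if no individual's risk changes. Programmatic interns are placed partly to increase testing and linkage, so this could work against the intervention arm.
- **Cumulative reading.** The count consists largely of people who defaulted before the outcome window, and it says little about months 4-9.
- **Current-default reading.** The measure may be sound, but Table 3 does not describe it.

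**Working it through.** **Inputs, summed over the 31 rows of Table 1**

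| Quantity | Total | Facility range |
|---|---|---|
| ART initiations per month (average) | 272 | 2 to 24 |
| On ART, July 2019 | 22,301 | 181 to 1,577 |
| Early default, July 2019 | 3,698 | 18 to 335 |

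**1. Early default against one month of initiations.**
- Overall: 3,698 / 272 = 13.6.
- Smallest: Lehurutshe Hospital, 24 / 8 = 3.0. Largest: Ottosdal CHC, 335 / 9 = 37.2. The median is 14.0.
- The ratio is above 1 at 31 of 31 facilities.

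**2. Could rounding, month boundaries or a broken row explain it?**
- Rounding: adding 0.5 to each monthly average leaves a smallest ratio of 24 / 8.5 = 2.8.
- Month boundaries: a 28-day window can straddle two calendar months. Against two months of initiations the overall ratio is 3,698 / 544 = 6.8 and the smallest is 24 / 16 = 1.5, still above 1 everywhere.
- The Agisanang row is garbled in the text available to me and was read as 7 initiated, 740 on ART, 76 early default. Without it the ratio is 3,622 / 265 = 13.7.

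**3. The section 5.1 percentage.**
- From Table 1's counts: 3,698 / 22,301 = 16.6% (facilities 6.1% to 40.5%).
- Ceiling under Table 3 if every initiate of one month defaulted: 272 / 22,301 = 1.2% (facilities 0.8% to 4.4%). Allowing two months of initiates: 544 / 22,301 = 2.4%.

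**4. Could it be a cumulative total?**
- Ten months of initiations come to about 10 × 272 = 2,720, and 3,698 / 2,720 = 136%. The early-default count exceeds ten months of initiations at 22 of 31 facilities.
- A total reaching further back is not excluded. Even if every initiate defaulted, it would need 13.6 months of initiations overall and 37.2 months at Ottosdal CHC.
- Under that reading, months 4-9 could add at most 6 × 272 = 1,632 people across these 31 facilities, against 3,698 already counted in July 2019.

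**5. Does Table 1 favour another denominator?** Over new initiates, the same counts give 3,698 / 272 = 1,360% per month. Over patients on ART they give 16.6%. Changing only the denominator therefore produces impossible percentages.

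**6. Sensitivity to initiations under the literal reading.** At constant individual risk the measure is proportional to initiations / on ART. As an illustration, a 20% rise takes 272 to 326.4 and the ceiling from 1.22% to 326.4 / (22,301 + 54.4) = 1.46%, a relative rise of about 20%. The 20% is an assumption, not a protocol figure.

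**7. Effect of the six-month sum.** Section 7.1 sums numerator and denominator alike. At July 2019 levels, (6 × 3,698) / (6 × 22,301) = 16.6%, unchanged.

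**The case against.** The best defence is that the column in Table 1 is headed as a total, while its neighbours are monthly averages. A long-run total of people who missed treatment early would be compatible with the 28-day wording, and Table 1 cannot rule it out. This stands: the counts are impossible under Table 3 only on the monthly, same-period basis of section 5.1. It does not rescue the outcome, because a cumulative total is not a monthly measure and does not describe default during months 4-9.

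Secondly, the indicators are taken as routinely reported in both arms. If only the Table 3 wording is wrong, the computed comparison does not change. If the report counts people currently in default, the interns' tracing work could lower it, and its average over months 4-9 would be a legitimate outcome. This also stands, but the protocol does not say that this is what is counted.

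Thirdly, the mechanical rise with initiations applies only under the literal reading, which Table 1 makes doubtful. Average initiations (272 per month) already slightly exceed new positives (264 per month), so better linkage alone has little room to raise initiations; more diagnoses would be needed. That limits the likely size of the distortion, not the mismatch between numerator and denominator.

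Two stronger readings are tempting and are not supported:

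- **That TX_Curr is shown to be the wrong denominator.** A wrong definition and a wrong denominator are alternatives. Table 1 is evidence against the definition, and with TX_Curr its counts give a coherent 16.6%.
- **That summing six months inflates the percentage by counting the same defaulter repeatedly.** People recur in the denominator as well, so the result is an average monthly prevalence.

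**Conclusion.** The point holds as an internal contradiction on a primary outcome. As a same-month count, the Table 3 definition of early default cannot produce the Table 1 figures: 3,698 against 272 initiations per month, or 16.6% of patients on ART against a ceiling of about 1.2% (2.4% if two months of initiates are allowed). The gap is present at every facility.

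The conclusion assumes that July 2019 initiations were near the ten-month average and that the Table 1 column is the same indicator as ART Default Early in Table 3. Which explanation is true cannot be settled from the protocol. The denominator is a mismatch only if the 28-day wording is correct.

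Table 1 has no late-default column, so nothing here tests that measure. Its definition uses the same 28-day cut from initiation and needs the same check.

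**What to change.** Before randomisation, ask the team that produces the monthly report what early and late default count: the reference date, and whether the figure is new events, people currently in default, or a cumulative total. Replace both Table 3 definitions with the answer, then match section 5.1 and the aggregation in section 7.1:

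- **Time since initiation:** divide by patients initiated in the same window.
- **People currently in default:** keep patients on ART as the denominator, use either the months 4-9 average or the month-9 prevalence, and state whether defaulters are included in the denominator.
- **Cumulative total:** use only new defaulters arising in months 4-9.

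The cost is one query and a few lines in Table 3 and sections 5.1 and 7.1. The Table 4 power calculation concerns HIV testing and is unaffected.
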